3.1 Type/Design of Trial

This is a phase 3, 12-week, multicenter, randomized, double-blind, placebo-controlled, fixed-dose trial designed to assess the efficacy, safety, and tolerability of brexpiprazole compared with placebo. Subjects will be randomized in a 2:1 ratio to brexpiprazole or placebo. Within the brexpiprazole arm, subjects will be further randomized in a 1:2 ratio to 2 mg/day or 3 mg/day, to explore the efficacy, safety, and tolerability of 2 mg/day and 3 mg/day brexpiprazole versus placebo.

The trial consists of a 2- to 42-day screening period, a 12-week double-blind treatment period, and a 30-day post-treatment safety follow-up period. In addition, for all subjects who terminate early from the trial, attempts will be made to collect data on mortality status by telephone contact with the subject's caregiver at Week 16. See Figure 3.1-1 for a schematic of the trial design and Table 3.7-1 for the Schedule of Assessments.

This trial will be monitored by an independent Data Monitoring Committee (DMC) (Section 3.7.8). The DMC will periodically monitor safety based on a predetermined schedule. In addition, an interim analysis of efficacy data is planned during the course of the trial, and will be performed by the independent DMC. The sponsor will remain blinded to the observed results of the interim analysis, and will only receive recommendations as per the interim analysis plan and DMC Charter. The details of the DMC structure and its roles and responsibilities will be documented in a DMC Charter.

The trial is organized as follows:

Screening Period

The screening period will range from 2 days up to 42 days, with the goal of completing all screening activities within 30 days, if possible, and will begin when the informed

consent form (ICF) is signed, prior to the initiation of any procedures. The screening period may be extended after discussion with and approval by the medical monitor. Additional requirements for obtaining informed consent from this vulnerable subject population are provided in Section 3.4.1. An eSource method will be used to obtain an identification (ID) number for each subject with documented consent.

The purpose of the screening period is to determine the subject's eligibility and to washout prohibited concomitant pharmacotherapy prior to randomization (refer to Section 4.1).

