Assessment	Screening ^a	Baseline (Day 0)	Week 2 (±2 days)	Week 4 (±2 days)	Week 6 (±2 days)	Week 8 (±2 days)	Week 10 (±2 days)	Week 12 or ET ^b (±2 days)	Follow- up ^c (+2 days)	Week 16 ^d	Notes
Prolactin (blinded)	X							X			Section 3.7.5.2
TSH with reflex to free T ₄ if abnormal	X										Section 3.7.5.2
HbA _{1c}	X							X			Section 3.7.5.2
PT, aPTT, and INR	X							İ			Section 3.7.5.2
Urine pregnancy test (women of childbearing potential) only	X							X			Section 3.7.5.2
ECG	X	X				X		X			Section 3.7.5.4
Urine drug screen and blood alcohol test	X										Section 3.7.5.2 Section 4.2
MMSE	X	X						X			
Sheehan-STS	X	X						X			Section 3.7.5.5.4
Extrapyramidal symptoms scales (SAS, AIMS, BARS)		X						X			
Adverse events	X	X	X	X	X	X	X	X	X		Section 5
Pharmacokinetic sampling		X				X		X			Section 3.7.6.1.1
			I	I			I				
Concomitant medications	X	X	X	X	X	X	X	X	X		Section 3.7.4
Mortality status assessment										X	Section 3.7.1.5
OTHER PROCEDURES											
IMP dispensing		X	X	X	X	X	X				Section 8.4
IMP accountability		X	X	X	X	X	X	X			

aPTT = activated partial thromboplastin time; INR = International Normalized Ratio; PT = prothrombin time.

^aSee Section 3.7.1.1.

^bSee Section 3.1.

^cSee Section 3.8.3.2.

^dNote that this visit is 16 weeks postbaseline and only for subjects who terminate early from the trial.

^eIf a previous MRI or CT scan of the brain performed after the onset of symptoms of dementia is not available, then an MRI/CT scan of the brain should be performed during screening. In addition, a repeat MRI/CT scan of the brain may be requested to be performed by CST or the IAP in order to confirm eligibility.

^fIf a fasting blood sample was obtained at the screening visit and less than 14 days have elapsed since the screening visit, clinical laboratory tests (hematology, serum chemistry, and urinalysis) do not need to be repeated at the baseline visit.

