3.7.1 Schedule of Assessments

3.7.1.1 Screening

The screening period begins after informed consent has been obtained. All required assessments will be performed as described in the Schedule of Assessments (Table 3.7-1). Subjects will participate in screening activities from 2 days up to 42 days, with the goal of completing all screening activities within 30 days, if possible. The screening period maximum of 42 days may be extended after discussion with and approval by the medical monitor. After a subject has provided consent, sites will obtain a subject ID number for the subject by accessing eSource. Completion of screening activities may require more than one visit.

Sites are required to communicate certain aspects of subject data during the screening period to CST and the IAP, as detailed in the Operations Manual. The CST and IAP must approve subject eligibility in order for the subject to be randomized. The following should also be noted:

- At the time of the subject's screening visit, the caregiver will be provided a document that will outline all caregiver responsibilities and their role in this trial. The caregiver should acknowledge and agree to undertake all the tasks designated by this protocol at the time of the informed consent process.
- The investigator must assess the capacity of the subject to provide informed consent during the screening period. Once this determination is made by the investigator, the options for obtaining informed consent from or on behalf of the subject must be followed as provided in Section 3.4.1.
- An assessment of all inclusion and exclusion criteria will be made to determine the subject's eligibility for the trial.
- A general clinical evaluation will be performed, including concurrent medical conditions, medical history over the past 2 years, and medical history beyond 2 years that is considered to be clinically relevant per the investigator's judgment.
- Washout from prohibited concomitant medications, if applicable, will begin after consent has been obtained (see Section 4.1).
- The eligibility review for each subject will be completed and submitted to CST and the IAP per the Operations Manual.
- The subject's caregiver or facility staff will complete a diary daily (if possible) after the ICF is signed, continuing through Week 12 or ET.

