4.1 Prohibited Medications

All subjects must discontinue all prohibited medications after signing the ICF during the screening period to meet the protocol-specified washout periods. The required duration of washout for selected prohibited medications is provided in Table 4.1-1. All other psychotropic agents not listed in Table 4.1-1 are prohibited and must be discontinued at least 24 hours before the first dose of IMP. Select CYP2D6 inhibitors and CYP3A4

inhibitors and inducers are listed in Table 4.1-2. The oral benzodiazepine therapy permitted during the trial is summarized in Table 4.1-3.

Tal	Table 4.1-1 List of Restricted and Prohibited Medications			
All	All other psychotropic agents not listed in the below table are prohibited and must be discontinued at least 24 hours before the first dose of IMP.			
	Medication	Prior to Randomization	During Double-Blind Treatment Period	
1.	Medications to treat Alzheimer's disease (cholinesterase inhibitors, memantine, or other cognitive enhancers)	Allowed provided that the dose has been stable for 90 days prior to randomization, and there is no decrease or discontinuation within 30 days prior to randomization.	Subject should remain on the same dose throughout the duration of the trial, except when medically indicated due to a change in the underlying medical condition.	
2.	Antipsychotics	7-day washout	Prohibited	
	High-dose antipsychotics exceeding the equivalent of ≥ 3 mg of risperidone (eg ≥ 5 mg of haloperidol, ≥ 375 mg quetiapine, ≥ 10 mg olanzapine, or local equivalent)	Not allowed within 90 days prior to screening .	Prohibited	
	Clozapine	Not allowed within 30 days prior to randomization.	Prohibited	
	Depot or long-acting injectable antipsychotic drugs	Washout of 1.5 times the dosing interval (according to the prescribing information) prior to randomization.	Prohibited	

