7.6.2 Clinical Laboratory Data

Summary statistics for changes from baseline in the routine clinical laboratory measurements, and prolactin concentrations will be provided. In addition, the incidence of potentially clinically relevant values identified using prospectively defined criteria for laboratory tests will be summarized.

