## 9 Safety Analysis

Standard safety variables to be analyzed include AEs, clinical laboratory tests, vital signs, electrocardiograms (ECGs), and physical examination. In addition, data from the following safety scales will be evaluated: MMSE score, assessments of suicidality (e.g, Sheehan-STS), and extrapyramidal symptoms (EPS; e.g, the Simpson-Angus Scale, abnormal involuntary movement scale [AIMS], and Barnes Akathisia Rating Scale [BARS]). Safety analysis will be conducted based on the Safety Sample. In general, baseline of a safety variable is defined as the last observation of the variable before taking the first dose of IMP, unless specified otherwise. Prospectively defined criteria will be used to identify potentially clinically relevant (PCR) abnormal values for clinical laboratory tests, vital signs, ECGs, body weight, and BMI.

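### The plan does not secure a prolactin baseline taken after antipsychotic washout: the prolactin row has no Day 0 sample, and the laboratory table contradicts that row

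*Protocol*

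**What the plan says.** Table 3.7-1 of the protocol gives prolactin its own row, "Prolactin (blinded", marked at Screening and at Week 12 or early termination only. Table 3.7.5.2-1 places prolactin in the serum chemistry column. Table 3.7-1 schedules serum chemistry at Screening, Baseline, Week 8 and Week 12 or early termination, and Protocol 3.5.4 counts prolactin among the routine laboratory tests.

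Footnote f to Table 3.7-1, repeated in Protocol 3.7.5.2, sets a waiver. If the screening sample was fasting and is less than 14 days old, "clinical laboratory tests (hematology, serum chemistry, and urinalysis) do not need to be repeated at the baseline visit".

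On washout, Protocol 3.7.1.1 says: "Washout from prohibited concomitant medications, if applicable, will begin after consent has been obtained". Protocol 4.1 is to the same effect: "All subjects must discontinue all prohibited medications after signing the ICF during the screening period to meet the protocol-specified washout periods". Table 4.1-1 requires 7 days for antipsychotics in general, and for depot products: "Washout of 1.5 times the dosing interval (according to the prescribing information) prior to randomization". On the length of screening, Protocol 3.1 says: "The screening period will range from 2 days up to 42 days".

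SAP 9 sets the baseline rule: "baseline of a safety variable is defined as the last observation of the variable before taking the first dose of IMP". Protocol 7.6.2 sets the use: "Summary statistics for changes from baseline in the routine clinical laboratory measurements, and prolactin concentrations will be provided". SAP 9.2.1 repeats this by treatment and visit. SAP 9.2.2 with Appendix 1 adds the incidence of treatment-emergent prolactin above the upper limit of normal (ULN).

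**The concern.** A change from baseline describes study treatment only if baseline reflects the state in which the subject starts it. Subjects may enter screening on an antipsychotic as long as the high-dose, multiple-drug and insufficient-response exclusions in Table 3.4.3-1 do not apply. If that drug raises prolactin and the screening sample is drawn before it clears, the recorded baseline is an on-drug value. Part of the change to Week 12 is then the old drug leaving.

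Two outputs are exposed. Mean change within each arm is pulled down, so a real rise from the washed-out level could appear as no change or a fall. Subjects already above ULN at screening may not be counted as treatment-emergent, which would understate that incidence. These are the prolactin figures that the SAP tabulates by treatment group.

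**Working it through.** No figure in the plan bears on this point, so there is nothing to reproduce. The check sets the passages side by side on each reading and then gives an illustration.

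**Reading A: the prolactin row governs.**
1. The only pre-dose sample is at screening.
2. Protocol 3.7.5.2 ties that draw to screening and to the time before study drug, but not to washout. Protocol 3.7.1.1 allows several screening visits. A draw before washout is therefore permitted but not prescribed. It is also natural, because the same blood decides laboratory eligibility.
3. Under the rule in SAP 9, the screening value is the baseline.

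**Reading B: prolactin belongs to serum chemistry.**
1. A Day 0 sample is scheduled and would normally be the baseline.
2. Footnote f waives it when the screening sample was fasting and is under 14 days old. Take the screening draw as day 0 and stop the antipsychotic that day. The 7-day washout is met from day 7, and 7 < 14, so a subject randomised from then through day 13 can lawfully have no Day 0 chemistry. Baseline is again the screening value.
3. On this route fasting glucose and lipids share the problem. The footnotes to SAP Tables 9.2.4-1 and 9.2.4-2 use the screening visit when Day 0 is unavailable.
4. The waiver does not apply to a non-fasting screening sample, which Protocol 3.7.5.2 allows, so Reading B exposes fewer subjects than Reading A.

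Neither reading guarantees a baseline after washout.

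**Illustration. All inputs except the arm sizes are assumptions.** Let p be the share of subjects whose screening sample was drawn on a prolactin-raising antipsychotic, and D the later fall in prolactin from stopping it. At 330 subjects randomised 2:1, the arms are 330 × 2/3 = 220 and 330 × 1/3 = 110.
- Shift in mean change, the same in expectation in each arm: -p × D.
- Expected shift in the brexpiprazole minus placebo difference: 0.
- Chance SD of that shift: D × sqrt(p(1-p)(1/110 + 1/220)).

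| p | D (ng/mL) | Within-arm shift (ng/mL) | Chance SD, between arms (ng/mL) |
|---|---|---|---|
| 0.1 | 10 | -1 | 10 × sqrt(0.09 × 0.01364) = 0.35 |
| 0.2 | 20 | -4 | 20 × sqrt(0.16 × 0.01364) = 0.93 |
| 0.3 | 20 | -6 | 20 × sqrt(0.21 × 0.01364) = 1.07 |
| 0.4 | 40 | -16 | 40 × sqrt(0.24 × 0.01364) = 2.29 |

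Over p from 0.1 to 0.4 and D from 10 to 40, the within-arm shift runs from -1 to -16 ng/mL and the chance SD from 0.35 to 2.29 ng/mL.

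**The case against.** The strongest reply is that this is a descriptive laboratory summary with a concurrent placebo arm. Washout precedes randomisation, so both arms carry the same artefact in expectation, and no prolactin test or powered contrast is planned. That stands. It limits the point to within-arm figures and to extra noise in an informal comparison.

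The reply also bears on stronger conclusions that a reader might draw:
- *That no prolactin sample is scheduled between washout and first dose.* The tables conflict. The dedicated row is more specific and probably governs, but the serum chemistry listing implies a Day 0 draw.
- *That the screening sample is always taken before washout.* The draw time within screening is not fixed.
- *That footnote f makes matters worse under the prolactin row.* The footnote covers hematology, serum chemistry and urinalysis, so it reaches prolactin only if prolactin is part of serum chemistry.
- *That subjects above ULN at screening cannot count as treatment-emergent.* SAP Appendix 1 gives a bare threshold for prolactin, and SAP 9.2.2 does not define treatment-emergent for laboratory values, whereas Table 9.4-1 does define new onset for QT and QTc. Understatement is possible, not certain.
- *That the treatment comparison is biased.* Randomisation protects it in expectation.

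The size is also unknown. The antipsychotics named in the exclusion criteria mark a dose threshold; they do not show how many enrolled subjects were taking such drugs.

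**Conclusion.** The concern holds in limited form. The two tables disagree on whether a Day 0 prolactin value exists, and neither reading secures a baseline after washout for every subject. Where a subject enters on a prolactin-raising antipsychotic and is sampled before it clears, within-arm change to Week 12 combines washout with study treatment, and the incidence above ULN may be understated. Only those subjects are affected. Their number and the size of the fall are not in the documents, so the illustrated shift of -1 to -16 ng/mL shows a possible range and is not an estimate. The brexpiprazole minus placebo difference remains unbiased in expectation, with added noise. The primary and key secondary endpoints are unaffected. This is more than a missing detail, because the affected summaries are the ones that the SAP reports and the remedy is cheap.

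**What to change.** 1. Reconcile Tables 3.7-1 and 3.7.5.2-1 by scheduling prolactin at Baseline (Day 0), where blood is already drawn for pharmacokinetics, and name that value as the prolactin baseline in SAP 9.2.1.
2. Do not apply the footnote f waiver to subjects whose antipsychotic was stopped after the screening draw. This protects fasting glucose and lipids as well.
3. Where no Day 0 value exists, footnote that baseline is the screening value. Present prolactin change and the incidence above ULN by antipsychotic use in the 30 days before consent or during screening. Protocol 3.7.4 already requires medications to be recorded from 30 days before consent. This step is possible even if sampling is complete.
4. In SAP 9.2.2, state whether a prolactin value above ULN must be new relative to baseline to count as treatment-emergent.

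The cost is one further blinded assay per subject, probably in a separate tube because the pharmacokinetic tubes contain heparin, a baseline panel for the few who lose the waiver, and minor programming. No dose or washout rule changes.

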3.7.1 Schedule of Assessments

3.7.1.1 Screening

The screening period begins after informed consent has been obtained. All required assessments will be performed as described in the Schedule of Assessments (Table 3.7-1). Subjects will participate in screening activities from 2 days up to 42 days, with the goal of completing all screening activities within 30 days, if possible. The screening period maximum of 42 days may be extended after discussion with and approval by the medical monitor. After a subject has provided consent, sites will obtain a subject ID number for the subject by accessing eSource. Completion of screening activities may require more than one visit.

Sites are required to communicate certain aspects of subject data during the screening period to CST and the IAP, as detailed in the Operations Manual. The CST and IAP must approve subject eligibility in order for the subject to be randomized. The following should also be noted:

- At the time of the subject's screening visit, the caregiver will be provided a document that will outline all caregiver responsibilities and their role in this trial. The caregiver should acknowledge and agree to undertake all the tasks designated by this protocol at the time of the informed consent process.
- The investigator must assess the capacity of the subject to provide informed consent during the screening period. Once this determination is made by the investigator, the options for obtaining informed consent from or on behalf of the subject must be followed as provided in Section 3.4.1.
- An assessment of all inclusion and exclusion criteria will be made to determine the subject's eligibility for the trial.
- A general clinical evaluation will be performed, including concurrent medical conditions, medical history over the past 2 years, and medical history beyond 2 years that is considered to be clinically relevant per the investigator's judgment.
- Washout from prohibited concomitant medications, if applicable, will begin after consent has been obtained (see Section 4.1).
- The eligibility review for each subject will be completed and submitted to CST and the IAP per the Operations Manual.
- The subject's caregiver or facility staff will complete a diary daily (if possible) after the ICF is signed, continuing through Week 12 or ET.

3.7.1.2 Baseline (Day 0)

If the subject is found to be eligible for the trial during the screening period, all required baseline assessments will be performed according to the Schedule of Assessments (Table 3.7-1). The following should also be noted:

- Approval from CST and the IAP for randomization of subject will be verified.
- Inclusion and exclusion criteria will be verified.
- The investigator must determine if there have been any changes to the prior assessment of the subject's capacity to provide informed consent. If changes have been made, refer to the instructions detailed in Section 3.4.1.1.
- Diary recording will continue.
- The subject will take the first dose of the IMP from the assigned blister card on Day 1 (ie, the day after the baseline visit). The subject should take the IMP at approximately the same time each day, preferably in the morning, without regard to meals.

3.7.1.3 Double-blind Treatment Period

3.7.1.3.1 Weeks 2, 4, 6, 8, and 10

All subjects will be evaluated at Weeks 2, 4, 6, 8, and 10. Visits are to occur within \pm 2 days of the target visit date. All required evaluations will be performed as described in the Schedule of Assessments (Table 3.7-1). The following should also be noted:

- The investigator must determine if there have been any changes to the prior assessment of the subject's capacity to provide informed consent. If changes have been made, refer to the instructions detailed in Section 3.4.1.1.
- Diary recording will continue.
- IMP accountability will be performed.
- The subject will start taking the IMP from the assigned blister card the day after the clinic visit. The subject should take the IMP at approximately the same time each day, preferably in the morning, without regard to meals.

3.7.1.4 End of Treatment (Week 12)

All required evaluations will be performed as described in the Schedule of Assessments (Table 3.7-1). The Week 12 visit signifies the end of treatment for all subjects. Therefore, all subjects will undergo a complete evaluation at Week 12 (\pm 2 days). In addition, Week 12 or ET evaluations are to be completed for any subject withdrawn from the trial at any time, if possible. If a subject is withdrawn, every effort will be made to complete all of the Week 12 or ET evaluations prior to administering any additional

medications for the treatment of agitation or other prohibited medications. The following should be noted:

- Diary recording will be stopped.
- Final IMP accountability will be performed.

Subjects who complete the 12-week double-blind treatment period of Trial 331-14-213 may be eligible to enter a 12-week open-label extension trial.

If this trial is terminated early due to overwhelming efficacy from the interim analysis, subjects in this trial at the time may be offered entry into the open-label extension trial (Trial 331-201-00182) if they choose to participate.

3.7.1.5 Follow-up

All required assessments will be performed as described in the Schedule of Assessments (Table 3.7-1). All subjects, with the exception of those entering the optional open-label extension trial, whether they complete the trial or are withdrawn prematurely for any reason, will be followed up for a safety evaluation 30 (+ 2) days after the last dose of IMP during a clinic visit at either the investigator's site or residential facility, as applicable. If a clinic visit is not possible, the subject should be assessed by telephone with the subject and a caregiver. All AEs and concomitant medications will be recorded.

For all subjects who terminate early from the trial, all attempts will be made to collect mortality data by telephone contact with the subject's caregiver at Week 16.

